5.1.1 Cuddle technique

We will postpone the cuddle if the baby has any exclusion criterion before any cuddling episode. (section 7.12) If the baby has status epilepticus, we will post pone the cuddling episode until the status epilepticus is resolved.

5.1.1.1 Baseline

We will use the following standard operating procedure in the form of a check list (Appendix Fig 3). After obtaining consent, both parents will be invited for the cuddle and an appropriate time will be agreed between the parents and the nurses. If one parent consents to participate in the study and the other parent does not, we will offer the "CoolCuddle" to the parent consenting to the study after

Date 11.02.2020 Version 1.6

IRAS No. 257430 CoolCuddle protocol

ensuring that the parent with parental responsibility provides consent for the baby to participate in the "CoolCuddle". The research nurse will record the baseline data of temperature, respiratory, cardiovascular, amplitude integrated EEG (aEEG), pain score using the Neonatal-Pain Agitation Sedation Scale ³⁵, cerebral oxygenation monitoring using near infrared spectroscopy and blood gas over a 30-60 minute period prior to the cuddle. Infusion rates and medication doses will also be noted.

5.1.1.2 Cuddle

During a cuddle, the parent will be seated on a comfortable chair on one side of the cot. The chair may have reclining options or a footstool to enable foot elevation and a cushion/pillow for the lap will be available. One to two nurses will coordinate the process of transferring the baby from the cot to the parent along with the research nurse. We will ensure adequate space between the baby's cot and the parent's chair to allow a nurse to walk between the baby and the parent.

5.1.1.3 Preparation of baby (Fig 2) The nursing team will ensure all the tubes and catheters are secured appropriately noting the length at which they are attached to the baby. The tubes and catheters include endotracheal tube, central arterial and venous catheter and urinary catheter. Attachment of rectal probes and the aEEG leads will be checked. The infusion lines and the monitoring cables will be organised into two separate bundles using a Velcro strap ensuring adequate slack is available. Babies undergoing cooling are typically covered by the cooling blanket /wrap with a pillow for their head (to prevent the fluctuating water temperature in the cooling blanket affecting the superficial brain temperature)³⁶. The nursing team will clip the infusion lines and monitoring cables onto the edge of the cooling blanket. The aEEG head box will be clipped onto the cooling pillow using a Velcro strap. The urine collection container will be moved to the side where the parent is sitting and hung on to the side of the cot. The tube circulating water to the cooling jacket from the machine will be disconnected after clamping the tubes. Air entry on both sides of the chest will be checked and airway suction will be used if needed.

5.1.1.4 Moving the baby

The endotracheal tube and the ventilator circuits will be checked for any tangles. The nurse will stand at the bottom of the cot and support the baby's head and the cooling pillow with one hand and forearm approaching from the opposite side to the parents. The lower trunk and legs will be supported using the other arm with the infusion lines and the cables resting on the arm. When everyone is ready, the baby will be lifted from the bed maintaining the midline position. After a final check of the pathway of cables and lines ensuring there are no twists, the baby will be placed onto the parent's arms or on the lap or the top of a cushion/pillow (if used). If end-tidal carbon dioxide (CO2) monitoring is used, it will ascertain the patency of the endotracheal tube after transferring the baby onto the parent's arm or lap. Using the waveform morphology or the ventilator waveforms and air entry into the lungs will confirm

the endotracheal tube patency. The tubes from the cooling machine will be connected to the jacket to continue the cooling process. The cooling machine uses a servo control mechanism to maintain the set rectal temperature consistently²⁵. All monitoring of circulation and other physiological measures will be continued throughout the process as before the move. Once the baby is stable in the parent's arms, the baby will be turned to the side facing the parent maintaining the midline position. The Velcro straps that hold the infusion lines and the cables have a clip which will be clipped onto the parent's clothes.

The cuddle will continue for up to 2 hours but can be stopped earlier if the parent wishes or if any of the stop rules for cuddle are met. After the cuddle period, two nurses will move the baby back onto the cot following a similar process to that described above.

5.1.1.5 Stop rules for the cuddle

Cuddle will be stopped, and the baby transferred back to the cot, if any of the following occurs continuously for 5 to10 minutes during cooling without responding to any potential resolvable causes:

- 1. Rectal temperature < 30.0°C or >35.0°C
- 2. Mean blood pressure < 30mmHg or > 75 mmHg
- 3. Heart rate < 50 beats per minute
- 4. Heart rate >180 beats per minute
- 5. Oxygen saturation < 80%
- 6. Fraction of inspired oxygen >70%
- 7. Electroclinical or electrical status epilepticus

If any of the following occurs for greater than 20 minutes after any remediable causes are attended to:

- Rectal temperature between 30.0 and 32.9°C or between 34.1 and 34.9°C
- Mean blood pressure 10 mmHg below or above the pre-cuddle period
- Heart rate <20 beats per minute from the pre-Cuddle period or >20 beats per minute from the pre-Cuddle period
- Oxygen Saturation 80-88%
- Increase in Fraction of inspired oxygen by 20% above the pre-CoolCuddle period

or

• Medical or nursing concern that the infant is not adequately supported

If cuddle is undertaken during the rewarming period, the following stop rules will apply if they occur continuously for 5 to 10 mins despite attending to the potentially remediable actions:

- 1. Mean blood pressure < 30 mmHg or > 75 mmHg
- 2. Heart rate < 50 beats per minute
- 3. Heart rate > 180 beats per minute
- 4. Oxygen saturation < 80%
- 5. Fraction of inspired oxygen >70%
- 6. Electroclinical or electrical status epilepticus

The following stop rules will apply during the rewarming period, if they persist for greater than 20 minutes after any remediable causes are attended to:

- Rectal temperature greater than 4.0°C or less than 4.0°C from the pre-CoolCuddle period
- Heart rate 30 beats per min above or below the pre-CoolCuddle period
- Mean Blood pressure 20mmHg above or below the pre-CoolCuddle period
- Oxygen saturation 80-88% below the pre-CoolCuddle period
- Increase in Fraction of inspired oxygen by 20% above the pre-CoolCuddle period

Or

Medical or nursing concern that the infant is not adequately supported

We will have a 30-60 min pre-cuddle and post-cuddle epochs of data collection. A minimum of one cuddle episode per parents-infant pair during the four days of cooling therapy and rewarming period will be studied. Depending on the availability of nursing staff more frequent cuddle episodes will be encouraged. All cooled babies receive one to one nursing care in both the NICUs. An additional nurse is routinely involved in preparing drug infusions or delivering complicated care for babies receiving one-to-one nursing. Therefore, there will be no additional impact on the nursing workload.

Data collection

We will collect the demographic data of cooled infants and their parents, and maternal medical, social, pregnancy and labour history. The severity of encephalopathy, presence of multi-organ dysfunction, doses of drugs and continuous infusions received by the infant will be collected. During the precuddle, cuddle and post cuddle time periods the following physiology data will be collected on the case report form (CRF). Most of these data are stored digitally on the patient monitor every minute as part of routine care. These data can be used as a backup for the CRF and data at a sampling frequency of 1 minute can be obtained.

Physiology data

Date 11.02.2020 Version 1.6 CoolCuddle protocol

IRAS No. 257430

Every 5 minutes during pre-cuddle, cuddle and post-cuddle:

• Ventilation parameters: fraction of inspired oxygen, tidal volume, maximum peak inspiratory pressure, peak end expiratory pressure, mean airway pressure, inspiratory time, respiratory rate and oxygen saturation.

• Cardiovascular parameters: heart rate, blood pressure (the blood pressure transducer will be calibrated with the transducer at the level of the right atrium, every time the baby is moved)

• Surface and rectal temperature.

Other data to be collected

• End-tidal CO2 (if used in the NICU). Blood gas (measuring blood pH, pO2, pCO2, lactate, glucose) in the pre and post cuddle epoch. Blood gas is performed to ensure the babies are stable before and after cuddle in terms of oxygenation, ventilation and blood sugar. This is part of the standard care when babies are moved out of the incubator for longer periods.

• aEEG and NIRS (if used on the babies) will be marked at the onset of pre-cuddle, cuddle and post cuddle. aEEG will be analysed offline for continuity and seizures. NIRS data will be entered every 5 mins in the CRF.

- Adverse events
- Any instances of the following during the cuddling procedure:
 - o Accidental extubation
 - o Dislodgement of vascular catheters
 - Dislodgement of aEEG electrodes
 - o Needle-stick injury from aEEG electrodes

Data at discharge

.

We will collect data on mode and type of feeding. We will give mothers a mother-infant bonding (MIB) questionnaire and Edinburgh postnatal depression scale (EPDS) to complete around day 5-7 and at 8 weeks. We will collect father-infant attachment scores using a paternal postnatal attachment scale.

Data analysis

We will use the audio recordings of the talk aloud after each CoolCuddle episode to modify the CoolCuddle protocol. After the completion of "CoolCuddle" for each parent-infant pair, key investigators will use the talk aloud audio recordings and field notes made by the researchers to decide on the potential changes to the "CoolCuddle" protocol. We will aim to carry out the talk aloud

process with 4-6 parents-infant pairs. At the end of 3 months, a refined "CoolCuddle" protocol will be produced with involvement from the parent advisory group.

Stage 2: Effect of "CoolCuddle" protocol on the stability of cooling process and intensive care, and parents and healthcare staff opinion. (12 months)

We will use the refined "CoolCuddle" protocol and process on 20-24 cooled infant-parents pairs. The study participants will be recruited as for stage 1. Both parents will be invited for the cuddle. The intervention will be administered by nurses overseen by a research nurse.

All parents will be invited to be interviewed by the qualitative researcher and all who agree will be interviewed at an agreed convenient location or by phone/Skype. These interviews, with up to 20 parents, will explore their views on the refined CoolCuddle protocol and how best to roll it out to other NICUs. Interviews will take place after the 8 weeks questionnaires are collected and will mostly be by telephone so verbal consent will be recorded before each interview takes place. Parents will be sent an interview information sheet and consent form in advance of the interview date.

Staff involved in delivering the CoolCuddle protocol (6 nurses or doctors) at each site (St Michael's NICU and Southmead NICU) will also be invited to participate in focus groups meeting towards the end of Stage 2.

Data collection

The physiology data collection will be similar to stage 1; frequency and duration of data collection will be informed by the learning from the stage 1. The physiology data will be collected in the CRF and stored in the electronic databases. The questionnaire data including the responses from the EPDS, MIBS and paternal postnatal attachment scale will be stored in a REDCap database.

Data including the reasons parents did not want to consent for the study or cut short the cuddling episodes will be recorded.

The qualitative interviews will be audio-recorded, transcribed and anonymised.

Data Analysis

We will use descriptive statistics to report the parental questionnaire data and the adverse events. We will measure the mean or median (as appropriate) for the main physiological measures (see above). We will undertake three pairwise comparisons of pre-cuddle versus during-cuddle, during-cuddle versus post-cuddle and pre-cuddle versus post-cuddle using parametric t test or non-parametric Wilcoxon tests depending on the data distribution. We will derive the differences between the three

Date 11.02.2020 Version 1.6

23 of 37

IRAS No. 257430 CoolCuddle protocol

epochs (pre-cuddle, cuddle, and post-cuddle) and identify the magnitude of the differences, or variability which occurs. Using multilevel mixed-effects linear regression models, using data clustered by infant (or cuddle), we will assess if any difference in measures is likely to be due to chance (using a conventional level of statistical significance of p<0.05). We will also explore continuous monitoring of the physiological measures to establish variability over longer periods and the potential for adverse events. All data analysis will be conducted using the software SPSS or STATA.

We will compare our findings from the parental questionnaires with normative data. To compare parental bonding, we will collect these scores in our study to ensure they are in the satisfactory range following the "CoolCuddle". There are published normative data for mother-infant bonding scores³ and cut-offs for the father-infant attachment scores². We will compare our scores against these published data. We will also have detailed audit data on breastfeeding initiation and duration before September 2019 to compare with our study findings. If the cuddling process is stopped this will be treated as an adverse event and fully investigated to realise whether the problem is endemic, or modifiable and preventable.

Analysis of the qualitative interviews will be ongoing and iterative and will follow recognised thematic analysis procedures using NVivo software. Transcripts will be coded, and global themes developed from the codes. Two researchers will be involved in the analysis and will discuss any discrepancies and achieve agreement for a robust analysis. The findings will inform any changes that are needed to the final CoolCuddle protocol. The findings will also be discussed with the Parent Advisory Group to help us understand wider parent perspectives.

Stage 3: Modified "CoolCuddle" protocol along with data collection tool (3 months)

In this stage, we will finalise the "CoolCuddle" protocol producing a manual/standard operating procedure (SOP) of the process, monitoring required, training package for nurses, support for parents and follow up. The SOP will contain a data collection tool including data on adverse events and bonding scales to measure bonding at discharge and at 8 weeks. We will incorporate this with the existing southwest neonatal network cooling therapy pathway publishing it on the network website. During this stage, we will analyse all the data, prepare the NIHR report and manuscript.

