1 BACKGROUND

In the NHS, each year around 2100 infants (3/1000 live births) undergo cooling therapy to reduce brain injury following exposure to lack of oxygen and blood supply to the whole body around the time of birth⁴. This condition is called hypoxic-ischemic encephalopathy (HIE) and cooling therapy is the current standard treatment⁵ for infants with HIE. The cooling therapy involves cooling the whole body with a blanket or wrap that contains cold or warm water circulating through it and covering the baby's body. During cooling therapy, body temperature is maintained at 33-34°C for three days followed by 6-8 hours of rewarming to normal temperature of 36.5°C⁶. Most of the cooled infants often need intensive care including support for breathing, heart function and monitoring of brain activity including identifying and treating seizures⁶. As cooling therapy needs to be delivered in tertiary neonatal intensive care units (NICUs)⁵, babies with HIE born in peripheral hospitals will be transferred to tertiary NICU soon after birth and mothers who will be recovering from the delivery typically arrive a day later to the tertiary NICU. On arrival, parents often receive the news that their baby may die or suffer brain damage⁷. Furthermore, our national survey of neonatal intensive care units (NICU) offering cooling therapy showed that 95% of units do not allow parents to cuddle their babies during the entire cooling therapy period due to concerns of destabilising the cooling process and intensive care⁸. This practice has been reported to compromise parent-infant bonding by 80% of mothers in a recent cross-sectional survey⁹. The physical separation ensuing from transferring the baby to a distant NICU offering cooling therapy and the lack of emotional support after receiving the news that their baby may die or suffer brain damage further impedes the development of parent-infant bonding¹⁰. Impaired parent-infant bonding affects the establishment of breastfeeding¹¹, leads to emotional neglect in the newborn period¹², influences the emotional and cognitive development of children¹³, and results in postnatal stress or depression in parents^{14,15}, which if persistent may lead to behavioural problems in childhood^{16,17}. Given that the survivors of cooling therapy are already at a higher risk of neurodevelopmental disability with 22% having disability at 18 months¹⁸, and 18-20% having cerebral palsy^{19,20}and 30-40% having intellectual disabilities at school-age^{21,22}, compromised parent-infant bonding might contribute to or worsen the outcome in these vulnerable infants.

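### During cooling, a rectal temperature of exactly 35.0°C triggers no temperature stop rule, and the closed bands for temperature and saturation leave it unclear whether worse values count toward the 20 minutes

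*Protocol*

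**What the plan says.** Protocol section 5.1.1.5 ends a cuddle in the cooling phase on either of two tiers.

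- **Outer tier:** it applies when "any of the following occurs continuously for 5 to10 minutes during cooling" and the infant has not responded to correction of resolvable causes. For temperature the limit is "Rectal temperature < 30.0°C or >35.0°C"; for oxygen saturation it is below 80%.
- **Milder tier:** it is introduced by "If any of the following occurs for greater than 20 minutes after any remediable causes are attended to". For temperature it reads "Rectal temperature between 30.0 and 32.9°C or between 34.1 and 34.9°C"; for saturation, "Oxygen Saturation 80-88" per cent. The blood pressure rule in the same list is a change from baseline with no outer end: "Mean blood pressure 10 mmHg below or above the pre-cuddle period". Heart rate and inspired oxygen are also framed as changes from the pre-cuddle period.

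A non-numeric ground closes the list: "Medical or nursing concern that the infant is not adequately supported".

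The intended range is given in section 1: "body temperature is maintained at 33-34°C for three days". Section 5.1.1.4 allows a cuddle of up to two hours and describes servo-controlled cooling. Section 4.2 lists the frequency of stop-rule use among the outcomes, and the Stage 2 data analysis text counts a stopped cuddle as an adverse event to be investigated.

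**The concern.** The two temperature tiers should meet, so that every reading outside target falls under one of them. At the low end they do: the outer rule is below 30.0°C and the milder band starts at 30.0°C. At the high end the outer rule is strictly above 35.0°C and the milder band ends at 34.9°C, so 35.0°C falls between them.

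Secondly, because the milder temperature and saturation rules have two ends, an infant who moves beyond the outer limit has left the milder band. The text does not say whether those worse minutes count toward the 20.

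What is at stake is a numeric safety limit that staff at two sites should apply alike, and the count of stopped cuddles, which is reported as an outcome. Near 35.0°C, whether a cuddle is stopped and counted can turn on 0.1°C in either direction, which makes no clinical sense.

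**Working it through.** There is no figure in the plan to reproduce. The check applies the written rules to possible readings.

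**Inputs.** From section 5.1.1.5: outer tier T < 30.0 or T > 35.0°C, for 5 to 10 minutes; milder tier 30.0–32.9 or 34.1–34.9°C, for more than 20 minutes; saturation < 80% and 80–88% with the same durations. From section 1: target 33–34°C. From section 5.1.1.4: maximum 120 minutes. Assumptions: readings to 0.1°C, as the limits are written; 1-minute steps; no remediable cause outstanding, so the clock starts in minute 1.

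**Coverage, 28.0 to 37.0°C in 0.1°C steps (91 values).**

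| Tier | Values | Count |
|---|---|---|
| Outer | 28.0–29.9 and 35.1–37.0 | 20 + 20 = 40 |
| Milder | 30.0–32.9 and 34.1–34.9 | 30 + 9 = 39 |
| Target | 33.0–34.0 | 11 |
| No rule, outside target | 35.0 | 1 |

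40 + 39 + 11 + 1 = 91. If temperatures were read to 0.01°C, 32.91–32.99, 34.01–34.09 and 34.91–35.00°C would be uncovered as well. Saturation has no such gap, since below 80% and 80–88% meet.

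**Time to a temperature stop in a 120-minute cuddle.**

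- Steady 34.9°C: minute 21.
- Steady 35.1°C: 5 to 10 minutes.
- Steady 35.0°C: never.
- 15 minutes at 34.9°C, then 105 at 35.0°C: never. Only 15 minutes fall in the milder band, which is short of 20 whether time is added up or must be unbroken.

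**Closed band, using saturation.** Take m minutes at 84% (m = 1 to 20), then x minutes at 78%, too short for the outer rule, then 84% again. Here x is 1 to 4 if the outer rule acts at 5 minutes, or 1 to 9 if it acts at 10. An open-ended rule (≤ 88%) would stop every such trace in minute 21.

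- If band time is added up, the stop comes in minute 21 + x, a delay of x: 1 to 4 minutes (1 to 9).
- If band time must be unbroken, the stop comes in minute m + x + 21, a delay of m + x: 2 to 24 minutes (2 to 29), with the maximum at m = 20.
- If saturation falls to 78% and stays there after m minutes, the outer rule fires in minute m + 5 (or m + 10). At m = 20 the delay is 25 − 21 = 4 minutes (or 30 − 21 = 9).

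**With the milder rules open-ended** (T < 33.0 or T > 34.0°C), the outer set stays at 40 values, the milder rule alone covers 40, and none outside target is uncovered. The 34.9°C-then-35.0°C trace stops in minute 21 on either reading of the clock.

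**The case against.** The strongest reply is that the consequence is close to nil. Cooling is servo-controlled, nursing is one-to-one, and the reading would have to sit at exactly 35.0°C. Staff may stop on clinical concern, and section 7.4 lets the treating clinician discontinue a participant at any time. Physiology is recorded every 5 minutes whichever rule applies, and adverse events are only described. All of this stands and keeps the point minor. It does not supply the missing limit: the discretionary grounds carry no threshold, and setting rules either side of 35.0°C accepts that such temperatures can occur.

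On the closed bands, the 20-minute clause omits the word requiring continuity, so a cumulative reading is the more natural one, and a sensible nurse would count worse minutes. It is also fair that the milder blood pressure rule does not literally say 10 mmHg or more, so calling it open-ended involves some charity. This limb is therefore an ambiguity rather than an error, and the delays of 24 to 29 minutes need the less likely reading and an unluckily timed excursion.

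Finally, 35.0°C could equally go in the outer tier by writing ≥ 35.0°C, which would act sooner. That would close the gap too, but would leave the band counting unclear.

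**Conclusion.** The gap at 35.0°C is a plain fact of the text, and no other section of the protocol supplies a numeric limit there. It is a minor wording defect in a safety threshold, affecting one displayed value at the upper limit if temperatures are read to 0.1°C. The closed-band point is secondary: probably a delay of 1 to 4 minutes (1 to 9 if the outer rule acts only at 10 minutes), longer only for an intermittent trace under an unbroken reading. Sustained worsening is caught by the outer rule. No estimate or test of the physiological outcomes depends on either point, but the count of stopped cuddles can.

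**What to change.** Leave the outer limits unchanged. Write the milder cooling-phase rules, each for more than 20 minutes, as:

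- rectal temperature below 33.0°C or above 34.0°C;
- oxygen saturation at or below 88%.

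This places 35.0°C in the milder tier, as 30.0°C already is, and makes worse values count toward the 20 minutes. If the clinicians prefer the faster response at 35.0°C, the outer limit can be written as ≥ 35.0°C in addition. Carry the wording into the bedside checklist if it repeats these limits (it is not shown), and into the Stage 3 operating procedure.

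The cost is a wording amendment and possibly slightly more stopped cuddles, each counted as an adverse event under the protocol. No extra infants or measurements are needed.

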4.2 Outcomes

- Difference in mean/median and variability of surface and core temperature, ventilation, cardiovascular and neurophysiology parameters between the pre-cuddle, "CoolCuddle" and post cuddle epochs.
 - Day of life when oral feeds established
 - Mode and type of feeding at discharge and 8 weeks
 - Maternal mood assessed using Edinburgh postnatal depression scale¹ when the baby is 5-7 days of age and at 8 weeks.
 - Maternal-infant bonding assessed using Mother-infant bonding score³ when the baby is 5-7 days of age and at 8 weeks.
 - Father-infant attachment assessed using paternal postnatal attachment scale² at 8 weeks
 - Qualitative feedback on the "CoolCuddle" protocol
 - Incidence of adverse events including frequency of administering stop rules for "CoolCuddle", and dislodgement of endotracheal tube, central or peripheral arterial catheter, central venous catheter

5.STUDY DESIGN, METHODS OF DATA COLLECTION AND DATA ANALYSIS

This study will be a cohort study involving a controlled trial without randomisation design recruiting the cooled infants admitted to the NICUs of St Michael's and Southmead Hospital and their parents between September 2019 and January 2021.

5.1 Stage 1: Developing "CoolCuddle" protocol by refining existing cuddling technique using an iterative process (3 months)

Over 3 months, we will use the current family centred cuddling technique that we use for non-cooled babies receiving intensive care for babies receiving cooling treatment on 4-6 parents-infant pairs. We will attempt a minimum of one cuddle session per family up to 2 hours in length. We will refine the protocol by using 'talk-aloud' qualitative methods during each of the "CoolCuddle" sessions. Talk-aloud methods are used to gather data on usability and development of products and tasks³⁴. Talk-aloud methods involve participants describing their actions and how they go about completing the task. The audio-recordings made are used to improve the process through insights and modifications that arise during the session. A member of the research team will also observe all the "CoolCuddle" sessions and make field notes of changes made and actions taken.

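### Several cuddle stop rules in section 5.1.1.5 are miswritten: two are met by no change at all, one adds nothing to the <80% saturation rule, and the FiO2 rise has no stated scale

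*Protocol*

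**What the plan says.** Section 5.1.1.5 has one set of stop rules for cooling and another for rewarming. Each set has limits that apply after 5 to 10 minutes and a second tier that applies when a condition lasts more than 20 minutes after remediable causes have been dealt with. The lines at issue are all in the second tier.

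- Cooling, heart rate: "Heart rate <20 beats per minute from the pre-Cuddle period or >20 beats per minute from the pre-Cuddle period".
- Rewarming, saturation: "Oxygen saturation 80-88% below the pre-CoolCuddle period". The corresponding cooling line is simply a saturation of 80-88%, with no reference to the pre-cuddle value.
- Rewarming, rectal temperature: the line sets a greater-than and a less-than condition, both at 4.0°C and both measured from the pre-cuddle period, without saying above or below.
- Both lists, FiO2: "Increase in Fraction of inspired oxygen by 20% above the pre-CoolCuddle period".

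Two neighbouring lines give the direction properly: "Mean blood pressure 10 mmHg below or above the pre-cuddle period" (cooling) and "Heart rate 30 beats per min above or below the pre-CoolCuddle period" (rewarming). FiO2 is itself written in percent in the first tier ("Fraction of inspired oxygen >70"%).

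Stops are also study data. Section 4.2 lists "Incidence of adverse events including frequency of administering stop rules" among the outcomes, and the Stage 2 data analysis text treats a stopped cuddle as an adverse event to be investigated.

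**The concern.** These lines decide when an infant under intensive care is moved back to the cot, and their use is counted as an outcome. Each should have one meaning and be capable of separating a stable infant from an unstable one. As written, the heart-rate and temperature lines do not separate the two, the rewarming saturation line adds nothing to a rule already present, and the FiO2 line has two workable meanings.

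What is at stake is whether staff at two sites apply the same thresholds, and whether the reported frequency of stops has a clear definition.

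**Working it through.** There is no figure in the protocol to reproduce. The check is to evaluate each rule as a logical condition and compare it with its parallel line.

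**1. Cooling heart rate.** Let d be the heart rate during the cuddle minus the pre-cuddle rate.

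| Reading | Condition | d = 0 | d = -10 | d = -21 | d = +21 |
|---|---|---|---|---|---|
| Size of change | \|d\| < 20 or \|d\| > 20 | met | met | met | met |
| Signed change | d < 20 or d > 20 | met | met | met | met |
| Evidently intended | d < -20 or d > 20 | not met | not met | met | met |

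The first reading fails only at a change of exactly 20 in either direction, and the second only at exactly +20. Both are met by an unchanged rate. The intended form appears in the cooling blood-pressure line and the rewarming heart-rate line.

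**2. Rewarming saturation.** If S is the pre-cuddle saturation, a value 80 to 88 points below it lies between S - 88 and S - 80. Since S cannot exceed 100, the highest value that qualifies is 100 - 80 = 20%. From an assumed S of 95% the range is 95 - 88 = 7% to 95 - 80 = 15%. All such values are under 80%, and the <80% rule already acts on them after 5 to 10 minutes, sooner than this line's 20 minutes. Read literally, a saturation held between 80% and 88% during rewarming meets no numeric saturation rule.

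**3. Rewarming rectal temperature.** Let t be the temperature minus the pre-cuddle temperature. The condition becomes |t| > 4.0 or |t| < 4.0, or in signed form t > 4.0 or t < 4.0. With t = 0, both are met. The evident intent is t > 4.0 or t < -4.0. The figure itself also needs confirming. The Background gives a cooled temperature of 33-34°C and a rewarming target of 36.5°C, so the whole planned rise is 36.5 - 34 = 2.5°C to 36.5 - 33 = 3.5°C. A 4.0°C threshold is wider than that. The rewarming list has no other temperature rule.

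**4. FiO2 rise, both lists.** The percentage-point trigger is baseline + 20; the relative trigger is 1.2 × baseline. The protocol gives no FiO2 distribution, so these baselines are assumptions.

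| Baseline | +20 points | × 1.2 | Gap (points) |
|---|---|---|---|
| 21% | 41% | 25.2% | 15.8 |
| 30% | 50% | 36% | 14 |
| 40% | 60% | 48% | 12 |
| 50% | 70% | 60% | 10 |

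Above a baseline of 50% the percentage-point trigger passes 70% and the separate >70% rule takes over. The gap in effective thresholds then shrinks, reaching zero at 70 / 1.2 = 58.3%. The neighbouring change rules use the variable's own units (mmHg, beats per minute, °C), which favours percentage points, but no sentence says so.

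**The case against.** The strongest reply is that these are copy-editing slips. A heart-rate rule that is true for almost every value cannot be a working instruction. The parallel lines show what was meant, and the list is confined to problems persisting after remediable causes are attended to; an unchanged heart rate leaves nothing to remedy. The same can be said of the saturation and temperature lines. For FiO2, context points to percentage points and nothing in the protocol suggests a relative reading. Section 5.1.1.1 says staff work from a checklist (Appendix Fig 3), which is not in the text available and may be worded correctly. Each stop is investigated for cause, section 3 sends modifiable problems to the orange zone, and physiology is recorded "Every 5 minutes during pre-cuddle, cuddle and post-cuddle", so recorded episodes can be checked afterwards against either FiO2 reading.

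Most of this stands, and it sets the severity. It does not make the text right: these are safety thresholds that feed a listed outcome, and the correct wording is already available in the parallel lines. Three points limit the reply. Context favours a reading of the FiO2 rule but does not settle it. The 4.0°C figure cannot be confirmed from a parallel line. And later checking of recorded values cannot restore a cuddle that was cut short.

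A reader might infer that cuddles would be stopped for stable infants, that infants in rewarming are unprotected at saturations of 80-88%, or that the stop counts and the traffic-light decision will be distorted. The documents support none of these. Staff would be unlikely to stop for an unchanged heart rate, and medical or nursing concern is a stop rule in both lists. The FiO2 figures are differences between thresholds, not estimates of extra stops.

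**Conclusion.** Three rules are wrong as written: cooling heart rate, rewarming saturation and rewarming rectal temperature. A fourth, the FiO2 rise in both lists, is ambiguous, by 10 to 15.8 points at assumed baselines of 21% to 50%. The first three conclusions follow from the wording alone; the FiO2 sizes rest on the illustrative baselines.

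Severity is minor. The intended direction of the heart-rate and temperature lines and the intended form of the saturation line are evident. Harm is limited in both lists by the heart-rate limits of 50 and 180 beats per minute, saturation <80%, FiO2 >70% and the clinical-concern rule. For temperature in rewarming, the clinical-concern rule is the only evident backstop. No effect on the number of stops or on the study's conclusions is shown, and whether the bedside checklist repeats these lines is unknown.

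**What to change.** Reword section 5.1.1.5 as follows.

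- Cooling, heart rate: more than 20 beats per minute below or above the pre-cuddle value.
- Rewarming, saturation: oxygen saturation 80-88%, as in the cooling list.
- Rewarming, rectal temperature: more than 4.0°C above or below the pre-cuddle value, with the sponsor confirming that 4.0°C is the figure intended.
- Both lists, FiO2: a rise of more than 20 percentage points (0.20) over the pre-cuddle value, unless the sponsor confirms that a relative, 1.2-fold rise was meant.

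Make the same changes in the bedside checklist if it repeats these lines. The cost is the wording of four rules (five lines) and two confirmations from the sponsor, handled through the usual amendment route. No new data or analysis is needed.
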